3.6. Treatment Assignment and Blinding

This study has a single-dose phase and a multiple-dose phase and will include 4 separate age-specific cohorts of pediatric subjects, grouped according to age range (Table 3-1, in SAP Section 3.1).

The single-dose phase (in all 4 cohorts) will enroll subjects with Gram-negative bacterial infections and will confirm cefiderocol exposures in a minimum of 6 subjects prior to conducting a multiple-dose phase (in Cohorts 2, 3, and 4) in additional subjects.

This is a single-arm and open-label study.

3.7. Study Procedures and Flowchart

The study procedures and the times to be performed are summarized in the Time and Events Schedule, which is provided in the protocol Appendix 1.

This document is confidential.

4. Endpoints

4.1. Safety Endpoints

The following safety and tolerability endpoints will be evaluated:

- Adverse Events
 - Treatment-emergent adverse events (TEAEs), treatment-emergent serious adverse events (SAEs), treatment-related TEAEs and TEAEs leading to discontinuation of study drug
 - Special Situations – Abuse, Misuse, Overdose and Medication Error
- Vital signs (blood pressure, pulse rate, respiratory rate, body temperature)
 - observed and change from baseline values
- Clinical laboratory assessments
 - Routine lab tests (hematology, blood chemistry, urinalysis)
 - observed and change from baseline values
 - Estimated glomerular filtration rate (eGFR)
 - Urine pregnancy test
 - Microbiologic cultures
- Physical examination findings

4.2. Efficacy Endpoints

The following efficacy endpoints will be analyzed in the multiple-dose phase only at the EOT, the Posttreatment visit, and the EOS with cefiderocol alone:

- Clinical outcome (Clinical Cure, Clinical Failure, Indeterminate)
- Microbiological outcome per pathogen and per subject (Eradication, Persistence, Indeterminate)

4.3. Exploratory Efficacy Endpoints

The following exploratory efficacy endpoints will be evaluated for subjects in the multiple-dose phase at EOT, the Post-treatment visit, and EOS when treated with cefiderocol alone or in combination with SOC:

- Clinical outcome (Clinical Cure, Clinical Failure, Indeterminate)
- Microbiological outcome per pathogen and per subject (Eradication, Persistence, Indeterminate)

4.4. Pharmacokinetic Endpoints

The following pharmacokinetic endpoints will be evaluated:

- Plasma cefiderocol concentrations

4.5. Pharmacokinetic/Pharmacodynamic Endpoints

The pharmacokinetic/pharmacodynamic endpoints (parameters) will be specified in a PK Analysis Plan.

This document is confidential.

5. Analysis Sets

5.1. Safety Population

The Safety Population will be defined as all enrolled subjects who received at least 1 dose of cefiderocol. The Safety Population will be used for all safety analyses.

5.2. Pharmacokinetic Concentration Population

The Pharmacokinetic Concentration (PKC) Population will include all enrolled subjects who received at least 1 dose of cefiderocol and have at least 1 PK blood sample. This population will be used for the PK concentration listing.

5.3. Pharmacokinetic Concentration Summary Population

The Pharmacokinetic Concentration Summary (PKCS) Population will include all enrolled subjects who received 1 dose of cefiderocol in the single-dose phase and ≥ 4 doses of cefiderocol in the multiple-dose phase and those subjects who have at least 1 PK blood sample above the limit of quantification. This population will be used for the concentration summary, as well as for plotting of the concentration-time data and concentration data summary.

5.4. Intent-to-Treat Population (Multiple-dose Phase Only)

The Intent-to-treat (ITT) Population will be defined as all enrolled subjects who received at least 1 dose of cefiderocol.

5.5. Microbiological Intent-to-Treat Population (Multiple-dose Phase Only)

The Microbiological Intent-to-treat (MITT) Population will include all ITT subjects who have a baseline Gram-negative pathogen from any specimen from a baseline infection site.

5.6. Protocol Deviations

Major protocol deviations will be summarised, listed, and specified in the "Protocol Deviation Specifications Document" separately. A final list of major protocol deviations will be determined based on the data review prior to database lock.

This document is confidential.

6. General Aspects for Statistical Analysis

6.1. General Methods

All analyses and summaries will be produced using Statistical Analysis System (SAS®) version 9.4 or higher. All SAS programs used to generate analytical results will be developed and validated according to [REDACTED] programming standards and SAS validation procedures. Summaries will be presented by dose phase (single dose or multiple dose), cohort, and overall for each dose phase, unless otherwise specified.

Unless otherwise noted, continuous variables will be summarized using the number of nonmissing observations (N), arithmetic mean (Mean), standard deviation (SD), median, minimum, and maximum values as summary statistics.

Descriptive statistics for categorical/qualitative data will include frequency counts and percentages. The total number of subjects with a nonmissing value for the given variable will be used as the denominator for percent calculations, unless stated otherwise. All percentages will be presented with 1 decimal, unless otherwise specified. Percentages equal to 100 will be presented as 100, and percentages will not be presented for zero frequencies.

All subject study data, including data not appearing in tables, will be presented in subject data listings. Individual subject data, PK data, and any derived data will be listed by subject. All pre- and postdose assessments including repeat and unscheduled assessments will be included in the data listings.

No inferential statistical hypothesis testing will be performed in this study.

Summary statistics calculated for PK data are described in SAP Section 9 – Analysis of Pharmacokinetics.

6.2. Key Definitions

6.2.1. Baseline Definition

Baseline for weight, height: Baseline is the last available data within 4 days prior to Treatment Day 1 or on Treatment Day 1.

Baseline for other vital sign parameter: Baseline is the last available data prior to Treatment Day 1 pre dosing.

Baseline for Laboratory Evaluations: Baseline is the last available data within 4 days prior to Treatment Day 1 or on Treatment Day 1 for single dose phase, and are within 4 days prior to Treatment Day 1 or at Screening visit (excluding before 4 days prior to Treatment Day 1) in multiple dose phase.

Baseline for Gram-Negative Pathogen: Baseline pathogens will be determined from appropriate specimens from the baseline infection site collected within the 4 days prior to the first dose of cefiderocol in the multiple-dose phase of this study. If specimens are collected on multiple dates before the first infusion, the specimens collected on the latest date for each pathogen will be used to determine baseline pathogens. If there are more than one appropriate clinical specimens on the latest date, appropriate clinical specimens for the baseline will be selected following below priority.

This document is confidential.

1. When pathogens are identified as resent samples for the same subject, the larger req num ending with S02 will be used for analysis
2. When multiple records identified from same pathogen, same date, pathogen with the highest quantitative value will be considered
3. When multiple records identified from same pathogen, same date, pathogen with any valid minimum inhibitory concentration (MIC) for cefiderocol will be considered.

In case different Gram-negative pathogens are obtained from specimens from the baseline infection site, all of them will be considered as baseline pathogens.

Baseline for Microbiology Susceptibility: Microbiology Susceptibility tested for pathogens identified from IHMA. Baseline followed the baseline Gram-Negative Pathogen.

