In the single-dose phase, cefiderocol will be administered (in addition to SOC) at any time during the SOC treatment regimen. In the multiple-dose phase, cefiderocol will be administered on Day 1 (in addition to SOC), within 72 hours of the start of potentially effective treatment with SOC antibiotics for infection. Subjects will subsequently receive cefiderocol every 8 hours (q8h) for an expected 5 to 14 days; the total duration of cefiderocol administration will be determined by the investigator based on clinical assessment of each subject’s infection status. Each dose of cefiderocol will be administered IV over 3 hours. The infusion may be shortened if this is in the best interest of the subject and if approved by the sponsor via the Request for Shortened Infusion Duration Form. The single-dose phase will include only those subjects with normal renal function or mild renal impairment. The dose of cefiderocol for the single-dose phase will be determined based on body weight only; the maximum dose to be administered is not to exceed 2000 mg. The dose for the multiple-dose phase will be determined based on both body weight and renal function; the maximum dose to be administered is not to exceed 2000 mg. The SOC administered will be selected by the investigator based on the

suspected or confirmed pathogen(s) for the infection in accordance with local standards and can be modified at any time during the subject's participation in the study at the investigator's discretion. In the multiple-dose phase, if the subject's infection is confirmed to be Gram negative only before starting treatment, monotherapy with cefiderocol may be allowed.

End-of-treatment (EOT) assessments will occur within 24 hours after administration of cefiderocol (single-dose phase) or within 24 hours after administration of the last dose of study treatment (multiple-dose phase), or at early termination. A further clinical assessment will occur at a Posttreatment visit 7 (\pm 4) days after EOT (multiple-dose phase), which is analogous to a TOC and EOS time point, if microbiological samples are available. The EOS visit will occur 28 (+ 7) days after administration of cefiderocol in the single-dose phase or 28 (+ 7) days after administration of the last dose of study treatment in the multiple-dose phase; this visit may be performed on-site or via phone call. The study schematic including a schedule of assessments is provided in [Figure 3-1](#) and [Table 3-2](#).

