Multiple-dose Phase (Cohorts 2, 3, and 4): In the multiple-dose phase, subjects will be administered doses of cefiderocol infused IV over 3 hours, q8h, beginning on Day 1 and continuing for an expected 5 to 14 days (in addition to SOC), within 72 hours of the start of potentially effective treatment with SOC antibiotics for infection. The total duration of treatment with cefiderocol will be determined by the investigator based on clinical assessment of each subject's infection status. The dose of cefiderocol administered to each subject will be based on both body weight and renal function ([Table 5-2](#)). No more than 2000 mg of cefiderocol should be administered. After initiation of cefiderocol administration, cefiderocol doses may be adjusted based on changes in renal function as assessed by eGFR (using the Schwartz equation [[10](#)] if ≥ 3 months to < 1 year of age and modified Bedside Schwartz equation [[11](#)] if ≥ 1 to < 18 years of age) and according to the dosing recommendations for subjects with moderate or severe renal impairment ([Table 5-3](#)). See [Section 7.5.3.1.2](#) for eGFR calculations and ranges.

Shorter infusion times may be allowed in the multiple-dose phase if agreed on by the sponsor via the Request for Shortened Infusion Duration Form, and if in the best interest of the subject. Infusion volume adjustments by age will be provided in the pharmacy manual.

In special circumstances, treatment beyond 14 days may be allowed following review and approval of individual cases by the Shionogi medical monitor. To apply for this, a Treatment Extension Form should be completed and submitted to the Shionogi medical monitor on Day 12 or earlier (if over the weekend) to ensure continuity of treatment.

In the multiple-dose phase, if the subject's infection is confirmed to be Gram-negative only before starting treatment, monotherapy with cefiderocol may be allowed.

Table 5-1 Dosing Limits for Cefiderocol in Single-dose Phase: Subjects with Normal Renal Function or Mild Renal Impairment

Cohort	Single-dose Phase Dose		Infusion Time
	Body Weight		
	≥ 34 kg	< 34 kg	
1 (12 to < 18 years of age)	2000 mg	60 mg/kg*	3 hours
2 (6 to < 12 years of age)	2000 mg	60 mg/kg*	3 hours
3 (2 to < 6 years of age)	2000 mg	60 mg/kg*	3 hours
4 (3 months to < 2 years of age)	2000 mg	60 mg/kg*	3 hours

* **No more than 2000 mg of cefiderocol should be administered.**

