6.2.3. Appropriate clinical specimens

Appropriate clinical specimens are defined as sputum, tracheal aspirate, bronchoalveolar lavage (BAL) fluid, protected specimen brush, pleural fluid, lung biopsy for HAP/VAP, blood for BSI/sepsis/cIAI, or urine for cUTI. Specimens that were collected from other sites may be considered as appropriate specimen. This will be determined by the medical monitor. If the infection site is "other", it will be determined whether the specimen is an appropriate clinical specimen or not by medical monitor. The time window of the 4 days prior to the first dose of cefiderocol will be determined based on time unit, ie within 5760 min from the first infusion.

Eligibility of subjects into the MITT Analysis Population will be based on local lab results of baseline pathogens if the microbiological culture results are not sent to a central lab for confirmation or if central lab results are missing. In addition, in such a case, the local lab result will be used for analysis.

6.2.4. Day 1

Day 1 will be defined as the day of the first dose of cefiderocol.

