- Microbiological outcome per pathogen defined as the categories below:

HAP/VAP/cIAI and BSI/Sepsis:

- Persistence: Continued presence of the baseline Gram-negative pathogen from an appropriate clinical specimen.
- Indeterminate: No culture obtained from an appropriate clinical specimen or additional antibiotic therapy for the treatment of the current infection including missed sampling for reasons other than a successful clinical outcome.
- Eradication: Absence of the baseline Gram-negative pathogen from an appropriate clinical specimen. If it is not possible to obtain an appropriate clinical culture and the subject has a successful clinical outcome, the response will be presumed to be eradication.

cUTI:

- Persistence: A urine culture shows that the baseline Gram-negative uropathogen found at entry at $\geq 10^5$ CFU/mL grows to $\geq 10^3$ CFU/mL.
- Indeterminate: No urine culture obtained or additional antibiotic therapy for the treatment of the current infection including missed sampling.
- Eradication: A urine culture shows that the baseline Gram-negative uropathogen found at entry at $\geq 10^5$ colony forming units (CFU)/mL is reduced to $< 10^3$ CFU/mL.

Clinical response will be characterized based on an evaluation of clinical signs and symptoms by the investigator or designee. Clinical outcomes will be characterized at EOT, Posttreatment, and EOS if available.

The microbiological outcomes per subject determined by investigator will be entered in the eCRF. When the investigator confirms:

- that the subject experiences eradication of all baseline Gram negative pathogens then “Eradication” will be entered. For subjects with baseline infection other than cUTI who achieved clinical cure at corresponding visit, the response will be considered as Eradicated.
- that the subject experiences persistence of any baseline Gram-negative pathogen then “Persistence” will be entered
- that the subject experiences anything other than above then “Indeterminate” will be entered.

Emergent (ie, nonbaseline) pathogens will be considered separately, and will not affect the per-subject microbiological outcome.

This document is confidential.

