8.1.2. Microbiological Outcomes

For subjects treated with cefiderocol alone, the number and proportion of subjects in each category will be calculated for each time point (EOT, and Posttreatment visit and at EOS). Subjects will be presented by cohort and overall, for the MITT Populations. Note that the study is not designed to collect outcome data at EOS on all subjects, and summaries for microbiological outcomes will be underestimated due to indeterminate caused by missing data

For subjects treated with cefiderocol alone, the number and proportion of each category by each baseline Gram-negative pathogen will be calculated for each time point (EOT and Posttreatment visit and at EOS if available). Subjects will be presented by cohort and overall, for the MITT Population.

In addition, the proportion of eradication rate at Post treatment visit by each baseline pathogen and MIC will be calculated.

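### A pathogen already cleared by standard-of-care antibiotics before the first dose can be counted as eradicated under cefiderocol alone

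*SAP*

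**What the plan says.** **Baseline pathogen.** SAP 6.2.1 uses "appropriate specimens from the baseline infection site collected within the 4 days prior to the first dose of cefiderocol", and SAP 6.2.3 fixes the window in minutes, "ie within 5760 min from the first infusion". When there are several pre-dose dates, SAP 6.2.1 says that "the specimens collected on the latest date for each pathogen will be used to determine baseline pathogens". It does not say what a later negative pre-dose culture does to a pathogen that grew earlier.

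**MITT.** SAP 5.5 admits ITT subjects with a "baseline Gram-negative pathogen from any specimen from a baseline infection site". It has no condition on culture status at the first dose.

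**Earlier treatment.** Under Protocol 3.1, multiple-dose subjects start cefiderocol "within 72 hours of the start of potentially effective treatment with SOC antibiotics for infection". Protocol 5.2 adds that, once the infection is confirmed as Gram-negative only before treatment starts, "monotherapy with cefiderocol may be allowed". No exclusion criterion in Protocol 4.3 bars earlier SOC.

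**Outcome.** Outside cUTI, SAP Section 8 defines eradication as "Absence of the baseline Gram-negative pathogen from an appropriate clinical specimen". It also presumes eradication when no suitable culture can be obtained and the clinical outcome is successful. In cUTI a post-baseline urine culture is needed.

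**Analysis.** SAP 8.1.2 states: "For subjects treated with cefiderocol alone, the number and proportion of subjects in each category will be calculated for each time point". The same section adds tables by baseline pathogen and an eradication rate by pathogen and MIC. No table is split by prior antibiotic exposure.

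**The concern.** Response when cefiderocol is given alone is the study's only secondary objective, and the group's label invites the reader to credit the result to cefiderocol. An eradication rate does that only if the pathogen was there to be eradicated when cefiderocol began. Here the baseline culture may predate the whole SOC course, and SOC may have cleared the organism before the first dose. Later absence is then scored in cefiderocol's favour.

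The tables by pathogen and MIC are exposed in the same way. An isolate cleared by SOC would appear as a cefiderocol success at its MIC, although cefiderocol never had to act on it. SAP 8.1.2 warns that missing data will make the EOS microbiological summaries too low, but it says nothing about this upward pull.

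**Working it through.** **1. The window against the SOC lead-in.** The plan's own figure reproduces: 4 days × 24 h × 60 min = 5760 min. The SOC lead-in is at most 72 h × 60 = 4320 min. The difference is 5760 − 4320 = 1440 min = 24 h. A qualifying specimen can therefore come from before the first SOC dose by up to 24 h, with the full 72 h of SOC between it and cefiderocol. Protocol 7.5.3.2 also lets cultures taken before consent be recorded and used as a basis for inclusion.

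**2. One child followed through the rules.**
- Up to 96 h before the first dose: an appropriate specimen from the infection site grows a Gram-negative pathogen.
- Up to 72 h before: potentially effective SOC starts and clears it.
- Hour 0: the infection has been confirmed as Gram-negative only, and cefiderocol is given alone.
- Posttreatment: the pathogen is still absent, or, outside cUTI, no culture can be obtained and the child is clinically cured.

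The pathogen is a baseline pathogen under SAP 6.2.1, the child is in MITT under SAP 5.5, and the outcome is Eradication under SAP Section 8, tabulated in SAP 8.1.2. No rule in either document interrupts this chain.

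**3. What the latest-date rule does.** It can be read in two ways. If it means the last date on which each pathogen grew, an earlier positive stands despite a later negative. If it means the latest specimens decide, a later negative removes the pathogen. The text nearby favours the first reading: tie-breaks 2 and 3 choose among records of the same pathogen, that is, positive records, and the next rule keeps every different Gram-negative pathogen found. The SAP does not settle it, so two programmers could build two different MITT populations. If the only pre-dose specimen predates SOC, both readings give the same result and the problem remains.

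**4. Size.** Let c be the share of baseline pathogens cleared before the first dose that stay clear and are assessed as such, and e the eradication rate among the rest.

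Reported rate = c + (1 − c)e. Bias = c + (1 − c)e − e = c(1 − e).

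The documents give neither c nor e for this group. Assumed values give these reported rates:

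| c | e = 0 | e = 0.5 | e = 0.7 | e = 0.9 |
|---|---|---|---|---|
| 0.1 | 10% | 55% | 73% | 91% |
| 0.2 | 20% | 60% | 76% | 92% |
| 0.3 | 30% | 65% | 79% | 93% |
| 0.5 | 50% | 75% | 85% | 95% |

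At e = 0.7 the bias runs from 0.1 × 0.3 = 3 points to 0.5 × 0.3 = 15 points. The e = 0 column is a limiting case that shows the mechanism, not a forecast. The only nearby figure is the 72.6% composite of eradication and clinical response in the adult cUTI study (Protocol 1.2). It is a different endpoint in a different population, so it does not estimate e here.

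**The case against.** The strongest reply is that efficacy in this study is descriptive. Protocol 7.7 calls the efficacy assessments deliberately non-rigorous and supplemental, efficacy did not drive the sample size, and nothing is tested. Prior therapies, SOC administration and cultures are all listed by subject, so a careful reader could find the exposed cases. This stands as a limit on importance. It does not remove the point: one reason Protocol 7.7 gives is concurrent SOC, which does not describe the group treated with cefiderocol alone, and a listing does not correct a tabulated rate.

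A reader might also infer four stronger things that the documents do not support:
- **That any specimen will do.** SAP 6.2.1 needs an appropriate specimen from the baseline infection site. The wider wording in SAP 5.5 is still confined to a baseline infection site.
- **That the result is fixed before dosing, whatever cefiderocol does.** Continued presence or regrowth scores as Persistence. Additional antibiotic therapy, or a missing urine culture in cUTI, scores as Indeterminate, which SAP 6.4.2 counts as nonresponse. Staying clear once SOC stops may itself depend on cefiderocol.
- **That clinical response is biased by the same rule.** Clinical cure rests on signs and symptoms, and the ITT clinical table does not use the baseline-pathogen definition.
- **That most children on monotherapy will have had SOC.** The documents allow this but do not say how often it will happen.

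**Conclusion.** The point holds for microbiological outcome. A pathogen cleared by SOC before the first dose, and absent afterwards, can be reported as eradicated under cefiderocol alone, because the plan neither requires its presence at first dose nor defines the group by earlier SOC. The direction for such pathogens is upward. The size is c(1 − e): 3 to 15 percentage points for assumed c of 0.1 to 0.5 with e = 0.7.

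This rests on three assumptions: that c is in that range, that cleared pathogens stay clear independently of cefiderocol, and that their outcomes are assessed. If no child on monotherapy had effective SOC first, c is zero and there is no bias. The plan as written would not show which case applies. The safety and PK objectives are untouched, so this is a change that should be made to the SAP, not a flaw in the study's main purpose.

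**What to change.** 1. **SAP 6.2.1.** State that a pathogen absent from a later pre-dose appropriate culture of the same site is flagged as not present at the last pre-dose culture. List these pathogens and report the eradication tables with and without them. Leave the MITT definition unchanged: one negative culture taken on SOC is not proof of clearance, so dropping such subjects outright would be open to dispute. Say how a subject with both flagged and unflagged pathogens is handled in the per-subject table.
2. **SAP 8.1.1 and 8.1.2.** Present cefiderocol-alone outcomes by prior antibiotic for the current infection, none versus any. Where cells are too small, give hours of prior potentially effective SOC by subject. The clinical tables are included so that both outcomes can be read against the same exposure, not because the baseline rule biases them.

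The two parts cover different subjects. The flag needs a second pre-dose specimen, which Protocol 7.5.3.2 requests only where possible. The exposure split reaches those with a single specimen taken before SOC.

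**Cost.** SAP wording, one listing and a table split, on data already collected under Protocol 6.1 and SAP 7.5.1. Conduct and treatment do not change. Cells will be small, since the cefiderocol-alone group is an unknown part of a multiple-dose phase planned for at least 30 subjects (3 cohorts × 10), and the reported eradication rate may be lower.

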6.3. Handling of Microbiologic Data

If a pathogen is identified from local laboratory data but it is not sent to a central laboratory, the name reported by local laboratory will be used for analysis. In this case, the minimum inhibitory concentration (MIC) will be treated as unknown.

If a pathogen name is different between the local and central laboratory, the name assigned by the central laboratory will be used for the analysis. However, if the sample sent to International Health Management Associates Inc. (IHMA) was reported as “unknown” or the sample was not sent to IHMA, pathogen will be considered as no growth and used for analysis.

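### The baseline cefiderocol MIC follows a record chosen by date and colony count first, so an untested isolate can displace a tested one and a valid MIC drops out of the MIC tables

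*SAP*

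**What the plan says.** SAP section 6.2.1 settles the baseline Gram-negative pathogen in steps. The first is the date: "the specimens collected on the latest date for each pathogen will be used to determine baseline pathogens". If more than one specimen remains on that date, "appropriate clinical specimens for the baseline will be selected following below priority". The list has three entries:

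1. Resent samples: "the larger req num ending with S02 will be used for analysis".
2. Count: "When multiple records identified from same pathogen, same date, pathogen with the highest quantitative value will be considered".
3. MIC, under the same opening condition: "pathogen with any valid minimum inhibitory concentration (MIC) for cefiderocol will be considered".

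Different Gram-negative pathogens are all retained, so the selection is among records of one pathogen.

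Susceptibility has no selection rule of its own: "Baseline followed the baseline Gram-Negative Pathogen". A record can lack an MIC. For a pathogen identified locally but not sent to the central laboratory, SAP section 6.3 says: "In this case, the minimum inhibitory concentration (MIC) will be treated as unknown".

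The selected MIC is used in two places. SAP section 7.2 summarises MIC50, MIC90, range and CLSI/EUCAST susceptibility (Tables 14.1.3.2.5 and 14.1.3.2.6). SAP sections 8.1.1 and 8.1.2 report Posttreatment outcome by pathogen and MIC (Tables 14.2.1.3 and 14.2.1.6); for the microbiological outcome, "the proportion of eradication rate at Post treatment visit by each baseline pathogen and MIC will be calculated".

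**The concern.** The rule does two jobs with one record: it identifies the baseline culture, and it supplies the baseline MIC. Date and colony count are reasonable criteria for the first job. For the second, a record without an MIC is of no use, yet having one is the last criterion considered. A tested isolate can be set aside for an untested one of the same pathogen, and nothing in the SAP goes back to recover the MIC.

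Several baseline isolates are foreseeable. Protocol section 7.5.3.2 asks, where possible, for specimens both before any antibiotic and again before study treatment. Protocol section 5.2 starts cefiderocol within 72 hours of potentially effective standard of care, and the baseline window is 4 days, or 96 hours. Both specimens can therefore fall inside the window.

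At stake are four descriptive tables drawn from a phase with a minimum of 30 children (SAP section 3.4), restricted to the MITT population and split by species and, for outcomes, by MIC. With cells that small, one lost MIC is visible.

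**Working it through.** The documents give no figure to reproduce here, so the check has three parts.

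**1. Apply the order literally.** The MICs (µg/mL) are hypothetical, and each row is two isolates of one pathogen in one child. The last column applies the order proposed under the fix: valid MIC, then latest date, then highest MIC.

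| Case | Records | SAP 6.2.1 | Proposed |
|---|---|---|---|
| A | earlier isolate 4; later isolate untested | no MIC | 4 |
| B | earlier isolate 8; later isolate 0.5 | 0.5 | 0.5 |
| C | same day: higher count untested; lower count 4 | no MIC | 4 |
| D | same day: higher count 0.5; lower count 8 | 0.5 | 8 |
| E | same day, equal counts: 0.5 and 8 | not settled in 6.2.1 | 8 |
| F | same day, equal counts: untested and 8 | 8 | 8 |

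The plan discards an available MIC in A and C, and its list gives no unique answer in E. The MIC criterion helps only in cases like F, where date and count do not separate the records. If the two values in B or D are exchanged, the plan selects 8. It does not look at the MIC value.

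**2. Chance of losing an MIC (assumed inputs).** Take two isolates of a pathogen that date or count separates, each lacking an MIC independently with probability m. The plan loses the MIC whenever the selected isolate lacks one, with probability m. With a valid MIC required first, it is lost only if both lack one, with probability m². The avoidable part is m − m².

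| m | Plan, m | Valid MIC first, m² | Avoidable, m − m² |
|---|---|---|---|
| 0.1 | 0.10 | 0.01 | 0.09 |
| 0.2 | 0.20 | 0.04 | 0.16 |
| 0.3 | 0.30 | 0.09 | 0.21 |

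With six such children (also assumed), the chance of losing at least one MIC is 1 − (1 − m)⁶ under the plan and 1 − (1 − m²)⁶ with a valid MIC first:

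- m = 0.1: 1 − 0.9⁶ = 0.47, against 1 − 0.99⁶ = 0.06.
- m = 0.2: 1 − 0.8⁶ = 0.74, against 1 − 0.96⁶ = 0.22.
- m = 0.3: 1 − 0.7⁶ = 0.88, against 1 − 0.91⁶ = 0.43.

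**3. Sensitivity of MIC90.** SAP section 7.2 calculates MIC50 and MIC90 only from 10 subjects per bacterium. By its definition, MIC90 at n = 10 is the 9th ordered value (0.9 × 10 = 9). With eight values of 1 and two of 8, MIC90 is 8; if one child's 8 is replaced by 1, the 9th value is 1. The reverse replacement moves it from 1 to 8. These values are invented. They show only that one child can move the statistic at the smallest reportable size.

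**The case against.** The case for leaving the rule alone has substance.

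- **The date step is ordinary.** Taking the last pre-dose value is the SAP's general convention for baseline, and the latest isolate best reflects what is present at first dose. This stands, and the fix keeps it among isolates that have an MIC.
- **The count step may act rarely.** Protocol section 7.5.3.2 requires quantitative growth specifically for urine, though it also says quantification results will be collected for cultures. Where no count exists, the third criterion applies directly and already prefers a valid MIC. This narrows case C but not case A.
- **Untested isolates are not the intention.** The same protocol section has all isolated pathogens stored for shipment to the central laboratory. SAP section 6.3 also has a sentence under which an isolate not sent there counts as no growth. On that reading it might never displace anything. That sentence sits awkwardly beside the unknown-MIC rule, and the two need reconciling. The third criterion in 6.2.1 itself presupposes that some records lack a valid MIC.
- **Ties may be settled elsewhere.** SAP section 6.5 uses the latest of several records at one visit that are equally close to the target day. It would settle case E only if it applies to baseline isolates and their times differ. A reader should not infer that ties are never resolved.
- **Consequences are limited.** There is no hypothesis testing, and SAP section 6.1 puts repeat assessments in the listings.

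Two stronger readings are tempting. One is that the rule favours susceptible isolates. It does not: it is blind to the MIC value, and no systematic bias is shown. The other is that it distorts target attainment or %fT>MIC at MICs up to 4 µg/mL. SAP sections 4.5 and 10 send those analyses to a separate PK Analysis Plan, and nothing in 6.2.1 says its selection governs that plan. The link would have to be confirmed there.

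**Conclusion.** The point holds as a gap in the derivation of the baseline MIC. Followed literally, SAP section 6.2.1 lets an untested later or higher-count isolate remove an available MIC of the same pathogen from four tables, and it does not say which of two valid MICs is used when date and count do not decide.

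The size is uncertain. The documents do not state how often a child has several baseline isolates of one pathogen, or how often an isolate lacks an MIC. The loss rates of 10% to 30% against 1% to 9% apply only to children with two such isolates and rest on the assumed m and on independence. The MIC90 shift is an illustration, not a forecast. Safety, PK concentrations and overall cure and eradication rates do not depend on the choice. The change is worth making because the rule gives a worse result than an easy alternative.

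**What to change.** In SAP section 6.2.1, give the susceptibility baseline its own rule for Tables 14.1.3.2.5, 14.1.3.2.6, 14.2.1.3 and 14.2.1.6. Among a subject's isolates of the pathogen in the 4-day window:

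1. restrict to those with a valid cefiderocol MIC;
2. take the latest date;
3. if more than one remains, take the highest MIC.

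Keep the colony-count rule for the culture that scores the cUTI outcome. State whether the latest-record rule in section 6.5 applies to baseline isolates, and reconcile the two statements in section 6.3 on isolates not sent to the central laboratory.

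The cost is a few lines of SAP text and one derivation, with no new data. It should be settled before database lock: protocol section 9.1 acknowledges that SAP changes in this open-label study may be informed by unblinded data. There are two downsides. The MIC will occasionally come from a slightly earlier or lower-count isolate than the one defining the baseline culture, and the highest-MIC tie-break may make the MIC distribution look slightly less favourable. Taking the highest MIC over the whole window regardless of date would go further and override the last-pre-dose convention; that is debatable and not needed here.
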